Cover Page for Clinical Trial Study

Official Title: Comparing the Effects of a Plush Toy Dog versus a Live Therapy Canine on
Prosocial Behavior and Emotional Regulation in Children with Autism Spectrum Disorder

NCT#: N/A

Date: March 13, 2025

Study Protocol

Clinical Study Description

The purpose of this project is to investigate the human-animal interaction (HAI) and bond (HAB) between a canine trained in therapy techniques or a canine plush toy and youth with autism spectrum disorder (ASD) during animal-assisted therapy (AAT) sessions. We seek to explore identified gaps in knowledge pertaining to AAT in pediatric ASD care management.

Specifically, we want to document human interaction between either a live canine or the plush toy canine during AAT sessions, evaluating behaviors observed during and after AAT sessions. Caregivers were given the option to enroll the child in the AAT study at the follow-up appointment after the diagnostic assessment was completed, or upon enrollment in the ASD program if the child had an ASD diagnosis. The study was conducted between June 2022 through August 2024. Each AAT study lasted between eight to 12 weeks, and caregivers had the option to re-enroll the child for the next study to continue addressing behavioral concerns.

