3. Is there a difference in HAI in the live canine group and the toy plush dog group?
4. Is there a difference in prosocial behavior observed during AAT sessions between the live canine group and the toy plush dog group?
5. Is there a difference in behavior after AAT sessions between the live canine group and the toy plush dog group?

Design and Statistical Analysis Plan

We used two human-animal ethograms to investigate human-animal interaction and bonding occurring during AAT sessions. Prosocial behavior and emotional regulation demonstrated by participants outside of AAT sessions were assessed by two self-report questionnaires completed by caregivers. SPSS and Microsoft Excel were used to calculate the analysis. Descriptive statistics were utilized to compare prosocial behavior and emotional regulation occurring apart from AAT sessions between the two groups. Poisson analysis was conducted to examine human-animal bonding and human behavior occurring during AAT sessions. Independent *t*-tests were used to analyze the differences in human-animal interaction between the two groups. The homogeneity of the variance (HOV) assumption between two groups was checked using Levene's test for equality of variances in SPSS program before conducting the *t*-tests analysis. Results of *t*-tests with adjusted degrees of freedom value were reported if the HOV was violated. The null hypothesis was set to reflect no significant difference in HAI between groups for the independent *t*-tests; therefore, a significant difference in the human-animal interaction and human behaviors regarding the inclusion or exclusion of the canine could be confirmed if the *t*-test results reject the null hypothesis. Cohen's *d* was used to report the effect sizes of the independent *t*-tests; values up to 0.20 were interpreted as small, 0.50 as medium, and 0.80 as large effect sizes. Analysis of variance was used to assess differences between the two groups in prosocial behavior and emotional regulation occurring apart from AAT sessions.

Methods

Demographic data; past, family, and social histories; and prior therapy evaluations were collected during the initial consultation for enrollment into the ASD program. Additionally, pet ownership in the family home was included in the analysis.

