Lastly, the Positive and Negative Affect Schedule (PANAS) was administered weekly to measure therapeutic effects occurring in everyday life outside of the AAT session. The PANAS is a 20-item questionnaire utilizing a 5-point Likert scale to assess positive and negative affect occurring the week prior to administration. Each domain has 10 items with scores ranging from 10 to 50, with lower scores reflecting lower levels of positive or negative affect and higher scores signifying higher positive or negative affect. Total scores on each scale are obtained by adding the scores for each item. Analysis of the PANAS demonstrates very good internal consistency reliability, with alphas ranging from 0.86 to 0.90 for Positive affect and from 0.84 to 0.87 for Negative affect.

Protocol Number: 2307483365
Investigator: [name]

Expiration Date: 10/10/2025
Last Approval Date: 10/11/2024

University of Arkansas System

Document Overview

Description: Human animal interaction between children and a live canine or toy plush dog
Explanation:
Organization Doc Num:

Protocol Summary

Protocol Number: 2307483365
Sequence Number: 3
Status: Active - Open to Enrollment
Expiration Date: 10/10/2025
Last Approval Date: 10/11/2024
Investigator: [name]

Protocol Details

Type: Expedited
Summary/Keywords:
Application Date: 09/21/2024
Reference ID1:
Reference ID2:
FDA Application No:
Title: Human animal interaction between children with ASD and a live canine or plush toy dog

Areas of Research

Code	Description
000001	All Research Areas

Organizations

Type	Organization	Address
Performing Organization	University of Arkansas	University of Arkansas [name] USA

Funding Source

Type	Number/Code	Source	Title
Internally Funded/ Unfunded Research	unfunded	N/A	

Protocol Number: 2307483365
Investigator: [name]

Expiration Date: 10/10/2025
Last Approval Date: 10/11/2024

Subjects

Subject	Count
Children	150

Investigators

Person Name: [name] **Role:** Principal Investigator
Units: CC012723 UAF | NURS | Department of Nursing **Affiliation:** Supervisor
Office [contact] **Mobile:**
Email: [contact]

Study Personnel

Person Name	Role	Affiliation	Email
[name]	Study Personnel	Non-Faculty	[contact]
[name]	Study Personnel	Student Investigator	[contact]
[name]	Study Personnel	Student Investigator	[contact]

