
- **How long are the procedures likely to take? Include duration and frequency.**

The A4A weekly therapy sessions will last about 30 to 60 minutes, with opportunities for participants to interact with the canine or toy plush dog intermittently throughout the session, depending on the therapy activity.

- **How will information be given to people to get their informed consent to participate in this research? Answers should include specific methods (e.g., verbal consent, information handout, online consent form, full consent form requiring signature documentation.) **Please note that consent materials -- from a script for verbal consent to full consent forms that require participant signature -- must be uploaded in the Notes and Attachments section.**

[name] will contact parents/guardians of potential participants to explain the AAT program and gage their interest. If interested, parents will come to the A4A clinic on the first floor of ECHP to meet the canine and sign the informed consent form. Verbal assent will be obtained from pediatric patients who are cognitively able to give it.

- **Does data collection rely on a scheduled event, such as a convention or specific date?**

No

- **How will your data be collected? Include all that apply: online, on paper/in person, audio and/or video recordings. **Please note that all data collection materials will need to be uploaded in the Notes and Attachments section. This includes: surveys, questionnaires, interview questions or anything that is given to or asked of a participant.**

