Assigned to Agenda	Renewal-001:	10/11/2024
Submitted to IRB	Renewal-001: Submitted to IRB	09/21/2024
Renewal Created	Renewal-001: Created	09/21/2024
Renewal Reminder Generated	Renewal Reminder Letter #2	08/20/2024
Renewal Reminder Generated	Renewal Reminder Letter #1	07/05/2024
Expedited Approval	Amendment-001: Approved	04/26/2024
Expedited Approval	Amendment-001:	04/26/2024

Protocol Number: 2307483365
Investigator: [name]

Expiration Date:
Last Approval Date: 10/11/2024

Actions

Description	Comments	Action Date
Assigned to Agenda	Amendment-001:	04/26/2024
Submitted to IRB	Amendment-001: Submitted to IRB	04/14/2024
Amendment Created	Amendment-001: Created	04/14/2024
Expedited Approval		09/19/2023
Assigned to Agenda		09/19/2023
Administrative Correction	Changing consent document format to PDF for approval watermark.	09/19/2023
Submitted to IRB	Submitted to IRB	09/05/2023
Specific Minor Revisions Required		09/05/2023
Delete Review	Online reviewer [name] has been deleted. Deletion reason - Reviewer has not responded in a reasonable length of time; review is being reassigned to another board member.	08/25/2023
Submitted to IRB	Submitted to IRB	07/30/2023
Protocol Created	Protocol created	07/29/2023

Review Comments

Protocol Number: 2307483365 **Sequence Number:** 3
Principal Investigator: [name]
Title: Human animal interaction between children with ASD and a live canine or plush toy dog
Committee Id: 200 **Committee Name:** IRB Expedited Review
Schedule Id: 45832 **Schedule Date:** 11/16/2024

Review Comments:

Positive and Negative Affect Schedule (PANAS-SF)

Indicate the extent you have felt this way over the past week.		Very slightly or not at all	A little	Moderately	Quite a bit	Extremely
PANAS 1	Interested	 1	 2	 3	 4	 5
PANAS 2	Distressed	 1	 2	 3	 4	 5
PANAS 3	Excited	 1	 2	 3	 4	 5
PANAS 4	Upset	 1	 2	 3	 4	 5

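### The PANAS has no defined baseline: with its one-week look-back, a form completed at or before the first session is pre-treatment, yet the plan neither sets such a form apart nor states any adjustment for it

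*Combined protocol and SAP*

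**What the plan says.** The Methods section states that the PANAS "was administered weekly to measure therapeutic effects occurring in everyday life outside of the AAT session" and that it is used "to assess positive and negative affect occurring the week prior to administration". The form itself agrees: "Indicate the extent you have felt this way over the past week". No PANAS administration is called initial or baseline, and the time of the first form relative to the first session is not given. The SDQ is treated differently. The same section gives it an initial version at study start and a follow-up version every four weeks.

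The Clinical Study Description says "Each AAT study lasted between eight to 12 weeks" and allows re-enrollment. The IRB Questionnaire puts sessions on a weekly schedule: "The A4A weekly therapy sessions will last about 30 to 60 minutes".

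For outcomes outside sessions, the Design and Statistical Analysis Plan says "Descriptive statistics were utilized to compare prosocial behavior and emotional regulation occurring apart from AAT sessions between the two groups", and later "Analysis of variance was used to assess differences between the two groups in prosocial behavior and emotional regulation occurring apart from AAT sessions". It names no time point, summary measure, change score, covariate or repeated-measures term. Participants are split between dog and plush toy with no method or ratio of allocation described.

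**The concern.** The look-back decides which week a PANAS score belongs to. A score from the week before the first session cannot differ between groups because of the dog. Entered as an outcome, it contributes no treatment effect to whatever summary it joins. Left out of the model, it is a lost chance to remove stable differences between children from the error term.

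The second loss matters more than usual here. Without a statement that allocation was random, the groups may differ in affect before treatment. An analysis of variance with no baseline term carries that gap into the answer to research question 5, on behavior after sessions. The authors separated baseline from follow-up for one caregiver questionnaire and not for the other, so a reader cannot tell what was intended for the PANAS.

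**Working it through.** The plan states no power, alpha, PANAS effect size or PANAS summary, so there is no figure of its own to reproduce. What follows is an illustration.

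**Inputs from the documents**
- Follow-up of 8 to 12 weeks (Clinical Study Description) with weekly forms (Methods), taken as K = 8 to 12 forms.
- Subject count of 150 (IRB Subjects table).
- Reference SD for Positive Affect of 7.2 (printed on the PANAS form; not a planning value).

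**Assumptions**
- The first form is pre-treatment.
- 75 children per group, all with PANAS data.
- A constant effect of 0.4 SD from the second form on.
- Equal correlation ρ of 0.5 to 0.7 between any two weeks.
- Two-sided alpha 0.05, two-sample t-test.

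**Step 1: dilution, if all K forms are averaged.** The effect retained is (K−1)/K.
- K = 8: 7/8 = 0.875, a loss of 12.5%.
- K = 12: 11/12 = 0.917, a loss of 8.3%.
- On Positive Affect, 0.4 × 7.2 = 2.88 points becomes 2.88 × 7/8 = 2.52 or 2.88 × 11/12 = 2.64.

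**Step 2: three analyses, in SD units**
- A, mean of all K forms: effect 0.4(K−1)/K, variance [1 + (K−1)ρ]/K.
- B, mean of the K−1 later forms: effect 0.4, variance [1 + (K−2)ρ]/(K−1).
- C, as B with the first form as covariate: effect 0.4, variance of B minus ρ².

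Worked case, K = 8 and ρ = 0.5:
- A: effect 0.35; variance (1 + 3.5)/8 = 0.5625; SD 0.750; standardized effect 0.467.
- B: effect 0.40; variance (1 + 3)/7 = 0.571; SD 0.756; standardized effect 0.529.
- C: effect 0.40; variance 0.571 − 0.25 = 0.321; SD 0.567; standardized effect 0.706.

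| K | ρ | A: all averaged | B: first dropped | C: dropped and covariate |
|---|---|---|---|---|
| 8 | 0.5 | 81.0% | 89.6% | 99.0% |
| 8 | 0.7 | 69.8% | 80.6% | 99.8% |
| 12 | 0.5 | 85.8% | 90.9% | 99.4% |
| 12 | 0.7 | 74.5% | 81.4% | 99.9% |

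**Step 3: where the gain comes from.** Dropping the first form (A to B) adds about 5 to 11 points. Using it as covariate (B to C) adds about 9 to 19 points. The covariate step is about half the total gain or more: for K = 8 and ρ = 0.5, 9.4 of 18.0 points; for K = 8 and ρ = 0.7, 19.2 of 30.0.

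**Step 4: a starting gap.** Suppose the groups differ by a stable 0.2 SD before treatment (assumed), which is 0.2 × 7.2 = 1.44 points on Positive Affect. Analyses A and B both carry the full 0.2 SD. In C the within-group slope on baseline is ρ, so the part remaining is 0.2(1−ρ): 0.10 SD at ρ = 0.5 and 0.06 SD at ρ = 0.7. Adjustment reduces the bias but does not remove it.

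**Step 5: when step 1 does not apply.** An analysis of the last week only, of each week separately, or of change from the first form has no such dilution. If the first form came a week after the first session, no form is pre-treatment and there is no PANAS baseline to use.

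**The case against.** A reader might infer that the first PANAS certainly precedes treatment, that it is pooled with the rest, and that the plan discards the baseline. The documents do not support any of these as fact. They give no date for the first form and no rule for combining weeks. The absence of a baseline term is silence, not a stated exclusion. Saying that a repeated scale measures therapeutic effect is also compatible with analyzing change from its first value.

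A reader might also take the rise to 99% as the cost of the look-back. It is not: step 3 shows that about half or more of it is the ordinary benefit of baseline adjustment.

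Nor is 75 per group firm. The 150 is an IRB count with no allocation ratio, and the IRB Questionnaire lists the PANAS for ages 9 to 14 while the research questions cover ages 2 to 18. Fewer children may have PANAS data.

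These objections stand, and they make the dilution conditional and the power figures illustrative. They do not answer the remaining gap. The plan gives the forms one role, sets none apart, and states a comparison with no baseline term for groups that may start apart. Analyses that would avoid the dilution exist, but the plan specifies none of them.

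**Conclusion.** The point holds in conditional form. It is established that the PANAS looks back one week, that the plan assigns every weekly form to therapeutic effect, and that the stated analysis of variance has no baseline term. It is not established that the first form is pre-treatment or that all forms are averaged, so this is not a demonstrated look-back error.

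If both conditions are met, the expected difference shrinks by 8.3% (12 forms) to 12.5% (8 forms). If only the first is met, the form still goes unused for adjustment under the analysis as written, unless change from it is analyzed. That costs precision and leaves any starting difference in the result. The power ranges rest on 75 per group, 0.4 SD, correlation 0.5 to 0.7 and 5% two-sided alpha, all assumed.

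**What to change.** State for each child when the first PANAS was completed relative to the first session, and which weekly scores enter the analysis. Then:

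- Define the PANAS completed at or before the first session of the child's first enrollment as baseline, and exclude it from the outcome. A form at the start of a re-enrollment block follows earlier sessions and is not a pre-treatment baseline.
- Compare groups on the later weekly scores with the baseline score of the same scale (positive or negative) as covariate, either by ANCOVA on the mean of the later scores or by a repeated-measures model.
- Do not use a missing-baseline indicator, which can bias the comparison when groups are not stated to be randomized. Make the adjusted analysis the one in children with a pre-treatment form, and report all children unadjusted as a sensitivity analysis.
- If no child has a pre-treatment form, say that the PANAS has no baseline.

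The cost is mainly wording and a re-run on forms already collected. One week fewer counts as outcome, and children without a pre-treatment form leave the adjusted analysis. Since the Clinical Study Description reports the study as conducted through August 2024, label the definition post hoc if PANAS results have already been seen.

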Participants were divided into two groups: one with a therapy canine and one with a plush toy dog. Therapy sessions lasted 30 to 45 minutes, depending on the age and ability of the participant. All participants, no matter their group, received the same therapeutic strategies, such as sensory integration therapy and seated activity with the therapist, who is a certified pediatric nurse practitioner. Sessions with the therapy canine started with five to 10 minutes of free play with the canine, followed by sensory integration therapy based on the child's identified sensory profile. Participants then entered the clinic room for 20 to 30 minutes of a seated activity in which the therapist who taught coping and socialization strategies to participants and caregivers. Sessions concluded with five minutes of play with the canine. Play activities include fetch, soccer, hide and seek, and puzzles. The canine was trained to lay under the table in the clinic room while the therapist was working with the participants. He would provide grounding, light pressure, and deep pressure therapy if the participant became anxious during the sessions. The seated work was recorded using two cameras to ensure visibility of the interactions between the participant and therapist, canine, and caregiver; participant vocalizations and verbalizations; and participant facial expressions. We used two human-animal ethograms to code behavior during sessions and two behavioral assessments to note behavior occurring after sessions. All sessions occurred in the clinic located on the university's campus. Demographic data including participant age, gender, race, ethnicity, referral source, prior medical diagnoses, age of ASD diagnosis, medications, and prior allied health, school, or psychological evaluations. The canine was certified as a therapy dog and service dog certified in 10 ASD service dog tasks at the time of the study. The canine was present during sessions to interact with children and assist them to practice and develop skills to address identified deficits in social-emotional and adaptive functioning, prosocial behavior, and emotional regulation. AAT sessions were recorded to code interactions at a later time.

Objectives

This study will address the following research questions:

1. How do children with autism ages 2 to 18 years interact with a live canine during AAT sessions?
2. How do children with autism ages 2 to 18 years interact with a toy plush dog during AAT sessions?

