Participants will be divided into 2 groups: one group will interact with the live canine while the other group will interact with a toy plush dog identical to the canine. [name] will use a variety of behavioral and developmental evaluations to identify concerns and provide strategies for home therapy to improve delays for both groups. The O'HAIRE Coding System and 3 AAT Observation ethogram will be used to observe and code human behavior during all sessions for both groups. Additionally, participants ages 8 years and older who are cognitively capable will be asked to self-report their emotional state before and after each AAT session using an 11-point Likert scale chart in the shape of a thermometer, with ranges from "no distress/totally relaxed" to "highest anxiety/stress that you've ever felt." A caregiver satisfaction and perspectives of AAT integration in therapy sessions will be assessed via surveys. Demographic data including participant age, gender, race/ethnicity, referral source, prior medical diagnoses, age of ASD or DD diagnosis, medications, and prior allied health or psychological therapies will be collected on all participants. [name] will incorporate AAT into the therapy sessions at the A4A clinic that are guided by the developmental, adaptive-functioning, and social/emotional assessments to target gross and fine motor skill, language, social, emotional, and adaptive-functioning development. Parents will be given handouts that are designed to address deficits identified by the assessments. The O'HAIRE Coding System will be used to observe and code human behavior during AAT sessions. Observable behaviors categories captured by the OHAIRE Coding System include Interactive Behaviors (Social Communication & Environmental Interaction), Emotional Display (Facial, Verbal), and Interfering Behaviors (Aggression, Overactivity, Isolation). The OHAIRE-V3 assessment will be used to calculate a human-animal bond score to quantify the interactions taking place between the pediatric participants and the animal. The ELAN Coding software will be used to achieve high inter-rater reliability through precise timing of observed interactions. The 3 AAT Observation ethogram assesses 26 canine behaviors during human-animal interactions. The ethogram is divided into three categories: affiliative indicators, moderate stress indicators, and high-stress indicators. All sessions will occur at the A4A clinic, which is located on campus in the Epley Center for Healthcare Professionals. The first interaction between the canine and the participant will focus on introducing the two and facilitating a bond through play, such as petting or brushing the canine, or throwing a ball. The canine will be present to interact with children as they are learning their skill for that week. For example, the canine will interact with the participant while the participant is learning a new skill, such as improvement in handwriting, and the participant will be able to interact and play with the canine if the participant focuses on completing the therapy assignment. Likewise, participants will earn points if they perform their therapy strategies at home and can use those points to interact and play with the canine at their next therapy session. Plush dog toys who look like the canine will be given to pediatric participants in both groups as incentive to perform their home therapies.

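### No allocation method is described, yet a significant t-test without covariates is taken to confirm a difference tied to the canine

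*Combined protocol and SAP*

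**What the plan says.** Group formation is described twice, each time in one sentence. The Clinical Study Description says: "Participants were divided into two groups: one with a therapy canine and one with a plush toy dog". The procedures answer in the Questionnaire says: "Participants will be divided into 2 groups: one group will interact with the live canine", with the other group using a plush dog. Neither place, nor any other, gives a sequence, ratio, stratification, matching or concealment, or says who made the assignment and when. The Clinical Study Description lets caregivers re-enrol a child but does not say which group the child then joins.

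On consent, the Questionnaire says that interested "parents will come to the A4A clinic on the first floor of ECHP to meet the canine and sign the informed consent form".

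On analysis, the Design and Statistical Analysis Plan says that independent t-tests were "used to analyze the differences in human-animal interaction between the two groups", and that on rejection of the null "a significant difference in the human-animal interaction and human behaviors regarding the inclusion or exclusion of the canine could be confirmed". For behaviour outside sessions it says: "Analysis of variance was used to assess differences between the two groups in prosocial behavior and emotional regulation occurring apart from AAT sessions". It also names a Poisson analysis for in-session bonding and behaviour, without model terms. The Methods section adds that pet ownership entered the analysis, but names no model for it.

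On timing, the Clinical Study Description dates the study June 2022 to August 2024. The Protocol Summary, last approved 10/11/2024, reads "Status: Active - Open to Enrollment".

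**The concern.** A two-group comparison supports a statement about the canine only if the groups would have been alike without it. Random, concealed assignment provides that on average. Where the method is not described, a reader cannot tell whether a difference comes from the dog or from which children ended up with the dog.

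The outcomes make this matter more than usual. The OHAIRE bond score counts talk, gesture, look, touch, affection and prosocial behaviour directed at the canine. Prior liking or fear of dogs, age and severity would plausibly shift these directly. No measurement of these in-session behaviours before the intervention is described, so change from baseline cannot separate the two explanations.

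If the plan is followed as written, a difference already present between the groups could be reported as a confirmed difference due to having the canine there.

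**Working it through.** The plan states no power calculation, significance level or allocation ratio, so it has no figure of its own to reproduce. The check has two parts.

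**1. What the planned tests can adjust for**

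- An independent t-test has one factor, the group. It cannot contain pet ownership or any other covariate.
- The analysis of variance and the Poisson analysis could carry covariates, but none is named for either.
- The pet-ownership sentence therefore cannot refer to the t-tests, and nothing ties it to another model.

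**2. How far a pre-existing difference moves the error rate**

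Inputs:

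- Number of children: 150 (Subjects table in the IRB record). No split is given. I assume 1:1, so 75 per group, and also show 50, 25 and 15 per group.
- Significance level: not stated. I assume two-sided 0.05.
- True effect of the canine: set to zero.
- Pre-existing difference between groups, b, in SD units: assumed 0.10, 0.20 and 0.30. The plan itself calls a d of up to 0.20 small.

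Formula: with n per group, the t statistic has df = 2n − 2 and noncentrality b × √(n/2). The false-positive rate is the probability that it falls beyond the two-sided 5% critical value.

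Example: at n = 75, √(75/2) = 6.124, so b = 0.20 gives noncentrality 0.20 × 6.124 = 1.22 on 148 df, and the rejection probability is 22.9%.

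| n per group | b = 0 | b = 0.10 | b = 0.20 | b = 0.30 |
|---|---|---|---|---|
| 75 | 5% | 9.3% | 22.9% | 44.6% |
| 50 | 5% | 7.9% | 16.8% | 31.8% |
| 25 | 5% | 6.4% | 10.7% | 18.0% |
| 15 | 5% | 5.8% | 8.3% | 12.5% |

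Differences of this size need no extreme imbalance:

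- A yes/no characteristic worth 0.5 SD on the outcome, differing by 20 percentage points between groups, gives 0.20 × 0.5 = 0.10 SD. At 40 points it gives 0.40 × 0.5 = 0.20 SD.
- A trait correlated 0.5 with the outcome and differing by 0.5 SD between groups gives 0.5 × 0.5 = 0.25 SD. At 75 per group the standard error is √(2/75) = 0.163, the shift is 0.25/0.163 = 1.53, and P(|Z + 1.53| > 1.96) = 0.33 by the normal approximation.

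The rate rises with sample size, because more children shrink the standard error and leave the bias where it is.

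**The case against.** **Silence is not proof.** A reader might infer that the groups were formed by family choice or by the investigator. The documents do not say so. They never call the assignment non-random, and removed consent pages cannot count as evidence either way. This objection stands, and the point is limited to what is described. It does not remove the point, because the design section and the procedures answer are both present, and the assignment method belongs there.

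**Meeting the dog at consent may affect only who enrols.** The consent answer describes one step for all interested parents. It does not say that the group is chosen then, or that families choose it. This also stands: the visit is a possible route for selection, with no stated safeguard, and no more than that.

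**The conclusion speaks of a difference, not an effect.** The research questions ask whether there is a difference, and the stated purpose is exploratory. That is fair as to tone. But the sentence ties the difference to including or excluding the canine and says that it could be confirmed, which invites a causal reading that an undescribed assignment cannot carry.

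**Pet ownership is already handled.** It is mentioned, and credit is due. How it enters is not stated, and it cannot enter a t-test.

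**It is too late to randomise.** A reader might take the open-enrolment status as showing that remaining children can be randomised. The June 2022 to August 2024 dates, the past tense of the analysis section and the cover date of March 13, 2025 point the other way. The documents conflict here, so randomisation can only be a conditional remedy. The analysis and wording changes do not depend on it.

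**Conclusion.** The point holds in this form: no random or concealed allocation is described, and the plan would still let a t-test without covariates confirm a difference tied to the canine. The stronger claims, that assignment was in fact non-random or that the groups in fact differ, are not supported by the documents.

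The table shows what could be at stake, not what happened. At 75 per group, a 0.20 SD imbalance would raise the chance of a false confirmation to between four and five times the assumed 5% (22.9/5 = 4.6). At 25 per group it would about double it (10.7/5 = 2.1). These figures rest on assumed group sizes, significance level, sidedness and imbalance; only the total of 150 is documented. If assignment proves to have been random and concealed, the expected imbalance is zero and the error rate returns to the nominal level.

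**What to change.** 1. **Analysis.** Replace the in-session t-tests with a regression comparing the groups, adjusted for age, pet ownership and one baseline severity or behaviour measure already collected. Use the initial SDQ where it is valid for age. The Questionnaire's data-collection answer gives its range as 3 to 16 years, against a study range of 2 to 18, so outside that range use a severity measure from the same list, such as CARS-2 (2 years to adulthood). Label the model post hoc if the data have been seen. Report baseline comparability by group.
2. **Disclosure and wording.** State how, when and by whom children were assigned, whether this came before or after meeting the dog, and which group a re-enrolled child joined. Unless assignment was random and concealed, call the study a non-randomised comparison and replace the confirmation sentence with wording of association.
3. **Enrolment status.** Reconcile the study dates in the Clinical Study Description with the status in the Protocol Summary. Only if enrolment continues, assign the remaining children from a concealed, computer-generated, blocked list and report that cohort separately.

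The cost of the first two items is a re-analysis of data already held and a few changed sentences. The third needs a short amendment and a list, if it applies. The price is a weaker claim for children already enrolled. Adjustment will not remove unmeasured confounding such as liking for dogs, and the SDQ is not a baseline for the in-session behaviours themselves.
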